## 6.2 Analysis methods

### 6.2.1 Primary analysis

The primary analysis will be an intention-to-treat analysis to compare the life-space assessment (LSA) between intervention and control groups at D30. LSA will be analyzed using GEEs with Gaussian distribution, exchangeable correlation structure and robust standard errors with small sample correction. This model accounts for the cluster design as well as for the small number of clusters and will be adjusted for the baseline LSA. The absolute difference between intervention group and control group will be presented with a 95% confidence interval (CI).

Continuous secondary outcomes will be evaluated likewise, adjusting for the baseline value if applicable. If outcome measures are non-normally distributed, we will apply an adequate distribution in GEE (e.g., gamma) or log-transform the outcome measure before analysis. Absolute differences between intervention group and control group will be presented with a 95% CI.

Binary outcomes will be analyzed using a GEE with a binomial distribution, a logit link, an exchangeable correlation structure and robust standard errors. Relative differences between groups will be presented as odds ratio with 95% CI.

Count outcomes will be analyzed using a GEE with a negative binomial distribution, a log link, an exchangeable correlation structure and robust standard errors. Relative differences between groups will be presented as rate ratio with 95% CI.

Time-to-event outcomes will be analyzed using a Cox regression model. To account for clustering, we will use shared frailties for clusters as well as cluster robust standard errors. Relative differences between groups will be presented as hazard ratio with 95% CI.

Categorical outcomes (discharge destination) will be analyzed using multinomial logistic regression with robust standard errors to account for clustering. Relative differences between groups will be presented as rate ratios with 95% CI.

Readmissions and emergency room visits will be analyzed as time-to-event outcomes, except if we notice that those outcomes often happen multiple times. In such case, we will analyze them as count outcomes.

Mortality and time to new institutionalization will be analyzed as time-to-event.

Falls will be analyzed as binary outcomes. If we notice that this outcome often happens multiple times, we will analyze it as a count outcome.

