## 2. Study Methods

### 2.1 Trial design

The INTOMOB RCT is a multicenter, cluster, randomized, controlled, superiority trial conducted in three hospitals in Switzerland, with a 180-day follow-up. The intervention is partially blinded. Outcome assessment and data analysis are blinded. Hospital wards are randomized in a 1:1 ratio to either intervention or control arm. Patients admitted to an intervention ward receive the intervention, while patients admitted to a control ward receive standard of care.

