### 2.2 Randomization

Since the INTOMOB trial is a cluster RCT, only the wards (i.e., the clusters) have to be randomized. Ward randomization was done in a 1:1 ratio and generated shortly before start of the RCT by a statistician from CTU Bern (University of Bern, [name]). The statistician only received identifiers and not the actual names of the hospitals and wards in order to stay blind. Randomization was blocked with block size two and stratified by hospital to have the same ratio of intervention and control wards in each study center. Randomization was also stratified by ward size (<30 beds or  $\geq$ 30 beds). HCPs working on an intervention ward and participating patients admitted to an intervention ward receive the INTOMOB intervention. HCPs working on a control ward and participating patients admitted to a control ward receive the control procedure.

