### 2.3 Sample size

See section 5.1 of the protocol, under “Sample size calculation for the RCT”. The calculated sample size includes a total of 274 patients (137 in each arm, and in 12 clusters in total).

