## 4. Statistical Principles

### 4.1 Confidence intervals and *P* values

All effect measures will be accompanied by a two-sided 95% confidence interval. All applicable statistical tests will be two-sided and will be performed using a 5% significance level.

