### 4.3 Estimands

#### 4.3.1 Primary outcome on the FAS

**Outcome of interest:** life-space assessment at 30 (+/-5) days

**Patient-set of interest:** full analysis set

**Handling of intercurrent events:** if the primary outcome is missing in more than 5% of patients, we will employ multiple imputation in the primary analysis and additionally perform an available case analysis as sensitivity analysis disregarding missing data.

**Population-level summary measure of outcome:** absolute difference with 95% confidence interval, computed using generalized estimated equations (GEEs) with Gaussian distribution, exchangeable correlation structure and robust standard errors with small sample correction.

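### SAP 6.2.1 says the primary GEE allows for the small number of wards, but the only measure given is an unnamed correction of the standard error; no t reference or degrees of freedom is stated

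*SAP*

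**What the plan says.** The trial randomizes wards, not patients (section 2.1: "Hospital wards are randomized in a 1:1 ratio to either intervention or control arm"), and section 2.3 gives the size as "137 in each arm, and in 12 clusters in total". Section 2.2 adds that "Randomization was blocked with block size two and stratified by hospital", and that ward size was a second stratification factor.

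For the primary outcome, section 6.2.1 specifies "GEEs with Gaussian distribution, exchangeable correlation structure and robust standard errors with small sample correction". The model "will be adjusted for the baseline LSA"; it has no term for hospital or ward size. The same section then states: "This model accounts for the cluster design as well as for the small number of clusters". The estimand in section 4.3.1 repeats the specification: "exchangeable correlation structure and robust standard errors with small sample correction". In both places the correction belongs to the standard error.

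Section 4.1 sets the level: "All applicable statistical tests will be two-sided and will be performed using a 5% significance level". Section 6.4 brings in multiple imputation with Rubin's rules if more than 5% of primary outcomes are missing. Section 6.7 allows Stata or R and names no command. Nowhere does the SAP name the correction, the reference distribution or the degrees of freedom.

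**The concern.** A sandwich standard error from 12 wards has two separate defects. It is too small on average, and it is itself a noisy estimate. A small-sample correction of the standard error deals with the first. The second calls for a wider reference distribution, usually t with degrees of freedom tied to the number of clusters. The SAP mentions only the first remedy and then says that the few-cluster problem is dealt with.

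Two things are at stake. If the analyst uses the usual large-sample normal reference, the primary test can exceed 5% and the 95% CI can under-cover. And the text leaves the primary P value open: analysts who choose different corrections, or z rather than t, all comply, although section 6.8 plans double programming of this very analysis. The point covers the LSA model and the continuous secondary outcomes analysed in the same way.

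**Working it through.** **Figure to be checked.** The stated figure is the two-sided 5% level (section 4.1). It cannot be reproduced from the SAP, because the test is not fully specified. What can be computed is the level under each reading.

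**Inputs from the SAP.** 12 wards, 274 patients (274/12 = 22.8 per ward), 1:1 allocation of wards; Gaussian exchangeable GEE with intercept, arm and baseline LSA (p = 3); three hospitals, used as strata but not modelled.

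**Assumed, because the SAP gives no values.** ICC 0.01, 0.05, 0.10; ward-size CV 0, 0.4, 0.7; share of between-ward variance lying between hospitals 0, 25%, 50% (3 hospitals with 4 wards each, 2 per arm).

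**Step 1, closed form.** Suppose the corrected standard error is unbiased and the Wald statistic follows t with *d* degrees of freedom. A cutoff of 1.96 then has true level 2·P(t_d > 1.96):

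- d = 11: 7.6%
- d = 10: 7.8%
- d = 9: 8.2%

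So an unbiased standard error alone does not give 5%. The 97.5% point of t(10) is 2.228, and 2.228/1.960 = 1.137, so a t(10) interval is about 14% wider.

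**Step 2, simulation under the null, no hospital variance.** There were 6,000 trials per setting, so the Monte Carlo standard error near 5% is √(0.05 × 0.95/6000) ≈ 0.3 points. Each trial was fitted with the primary model and several variance estimators. K/(K−1) and K/(K−p) multiply the sandwich variance by 12/11 and 12/9. Kauermann-Carroll, Fay-Graubard and Mancl-DeRouen adjust the residual products for leverage.

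Ward-size CV 0 to 0.4, ICC 0.01 to 0.10:

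| Correction | Normal reference | t(10) |
|---|---|---|
| None | 10.0–13.1% | – |
| K/(K−1) | 8.9–11.7% | 5.8–8.6% |
| K/(K−p) | 6.5–9.3% | 3.7–6.7% |
| Kauermann-Carroll | 7.6–9.3% | 4.7–6.8% |
| Fay-Graubard | 6.7–7.7% | 3.9–5.6% |
| Mancl-DeRouen | 5.4–6.4% | 2.9–4.2% |

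With a normal reference the corrected tests run from 5.4% to 11.7%, so CI coverage runs from 100 − 11.7 = 88.3% to 100 − 5.4 = 94.6%. At CV 0.7 the normal-reference levels rise to 6.6–7.1% (Mancl-DeRouen), 9.1–9.9% (Fay-Graubard), 10.2–12.3% (Kauermann-Carroll), 9.5–13.3% (K/(K−p)) and 12.4–16.6% (K/(K−1)).

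**Step 3, the same with hospital variance.** Arms are balanced within hospitals but hospital is not in the model, so the standard error carries variance that the design has removed from the comparison. With 25% to 50% of between-ward variance between hospitals and CV 0 to 0.4:

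| Correction | Normal reference | t(10) |
|---|---|---|
| K/(K−1) | 5.9–11.6% | 3.4–8.5% |
| K/(K−p) | 3.8–9.0% | 2.1–6.5% |
| Kauermann-Carroll | 4.7–9.4% | 2.6–6.5% |
| Fay-Graubard | 4.0–7.9% | 2.2–5.2% |
| Mancl-DeRouen | 3.1–6.1% | 1.6–3.8% |

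The low ends come from ICC 0.10 with a 50% hospital share. At ICC 0.01 with CV 0.4, hospital variance changes little.

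**Reading the tables.** The choice of correction and the choice of reference matter about equally. A t(10) reference brings Kauermann-Carroll and Fay-Graubard near 5% when hospitals are alike. It leaves K/(K−1) too liberal in many settings and makes Mancl-DeRouen conservative.

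**The case against.** The strongest reply is that the SAP never says a normal reference will be used. It names no z statistic, no cutoff of 1.96 and no software command. An analyst who uses t with few degrees of freedom also complies, and the sentence about the small number of clusters may be meant to cover that. This stands: the inflation is conditional on a reference that the plan leaves open. A reader might infer that the primary test will run at 6% to 10%, or that false positives will be twice as frequent as stated. The document does not support either as fact. The first takes the normal reference as given and one set of assumptions; the second takes the least adequate correction as well.

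The second reply is that stratifying by hospital without modelling it makes the test conservative and can cancel the inflation. This stands in part. Step 3 shows levels at or below 5% for some combinations, but up to 11.6% for others. The hospital share is unknown, so the effect cannot be relied on.

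The third reply is that t(10) may overshoot. It may: Fay-Graubard with t(10) falls to 2.2% in the most extreme setting. That is a cost of the fix, but it does not justify leaving the reference unstated.

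None of this removes the gap. If both z and t fit the text, the plan has not fixed its primary test.

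**Conclusion.** The point holds as a specification gap with a conditional consequence. Section 6.2.1 claims that the small number of clusters is accounted for, and what sections 4.3.1 and 6.2.1 specify is not enough to secure that. With 12 wards and a normal reference, the 5% test would run at about 5% to 12% depending on the correction. This rests on ward-size CV up to 0.4, ICC 0.01 to 0.10 and little between-hospital variance, all assumed. More uneven wards make it worse; a large hospital share of the variance shrinks or removes it. It should be settled before database lock, because it decides the P value and CI of the primary outcome.

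**What to change.** In sections 4.3.1 and 6.2.1:

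- Name the bias-corrected standard error, for example Kauermann-Carroll or Fay-Graubard. The simple K/(K−1) factor is not enough.
- State that the CI and P value come from a t distribution with cluster-based degrees of freedom, 12 − 2 = 10 for the model as written (wards minus the intercept and arm parameters). If a hospital or ward-size term is added, set the degrees of freedom again.
- Apply the same rule to the continuous outcomes analysed in the same way.

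In section 6.4, state that the finite complete-data degrees of freedom enter Rubin's rules, so that multiple imputation does not return the test to a near-normal reference.

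The change is to SAP wording only and needs no new data. The cost is a CI about 14% wider than with a normal reference, and a test that may be somewhat conservative if the hospitals differ a lot.

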### 5.4 Baseline patient characteristics

Table 1 shows the list of baseline characteristics to be summarized. Continuous and count variables are presented as mean with standard deviation or median with quartiles, as appropriate. Categorical variables are presented as absolute and relative frequencies. Those variables will be presented by randomization group (intervention vs. control).

Table 1: Baseline table.

Description	Variable	Type
Age	age	Continuous [years]
Sex	sex	Categorical: female, male

Description	Variable	Type
Body mass index	weight_kg/height_cm	Continuous [kg/m  ]
Hospital	Hospital	Categorical: Inselspital, HFR, KSB
Number of hospitalizations in the last 180 days before admission	hosp_previous_n	Count
Support: home care	homecare	Binary: yes, no
Support: household help	household	Binary: yes, no
Support: mobility aid at admission	mobility_aid	Binary: yes, no
Life-space assessment		
Barthel Index (ADLs)	barthel_total	Continuous [range 0-100]
EQ-5D VAS	eq5d5l_vas2_uk_eng	Continuous [range 0-100]
DEMMI	demmi_score	Continuous [range 8-100]
Main diagnosis	hosp_cause	List of diagnosis categories
Number of medications at admission	med_n	Continuous

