10) Hand-grip muscle strength at hospital discharge	Muscle strength	strength_dynamo1_discharge, strength_dynamo2_discharge, strength_dynamo3_discharge	Continuous	Best of three attempts
11) Level of activity during hospitalization (% in light, moderate, [very] vigorous)	Accelerometer output	accelero_activity_level [% in light activity], acelero_activity_level_2 [% in moderate activity], acelero_activity_level_3 [% in (very) vigorous activity]	Continuous	Continuous
12) Level of activity during hospitalization (intensity of movement: vector magnitude CPM)	Accelerometer output	Accel_vm_cpm	Continuous	Continuous
13) Fear of / concerns about falling at discharge, D30 and D180	Falls Efficacy Scale – International	fes_i_total_d30/d_180	Continuous [range 16-64]	Continuous
14) FRID prescribing at hospital discharge	Medication classes at discharge	med_frid_discharge	Binary (Yes/No)	Binary (yes/no)
15) FRID prescribing at hospital discharge, D30 and D180	Medication classes at D30-D180	med_frid_discharge_fu_d30, med_frid_discharge_fu_d180	Binary (Yes/No)	Binary (yes/no) and

16) Falls during hospitalization and within D30 and D180	Falls	falls_yn_discharge1 / falls_yn_d301 / falls_yn_d180 (1 => repeated instrument);	Binary (yes/no)	Sum the number of falls for the count analysis	Binary (yes/no) or count
17) New institutionalization at hospital discharge and within D30 and D180	New institutionalization	new_institutionaliza_v_11_d30/d180 instit_date_d30/d_180	Binary (Yes/No) Date		Time- to event
18) Discharge destination	Index hospitalization – discharge data	Discharge_destination	Categorical [home, family (not own home), rehabilitation, nursing home permanent, nursing home temporary, other hospital, other institution, acute geriatrics, palliative ward, same hospital other ward, ICU, death, other]		Categorical
19) Emergency room visits within D30 and D180	Emergency room visits	er_visit_yn_30d1 (1 => repeated instrument); for between D30 and D180: same variable with “_180” instead of “_30” Date: er_visit_date_30d1 / _180d1	Binary (yes/no) Date	Sum the number of readmissions for the count analysis	Time-to-event or count
20) Readmissions within D30 and D180	Readmissions	readmission_yn_30_d1 (1 => repeated instrument); for between D30 and D180: same variable with “_180” instead of “_30” Date: readmission_30d1 / _180d1	Binary (yes/no) Date	Sum the number of readmissions for the count analysis	Time-to-event or count

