### 6.2.3 Sensitivity analyses

We will use generalized linear mixed-effects models instead of GEEs to account for clustering. For outcomes measured at D30 and D180, we will use a repeated-measures mixed-effects model. Should a GEE model not converge, we will use a mixed-effects model for that specific outcome as the primary analysis approach.

Because cluster randomization may lack the excellent balancing in characteristics between groups seen in individual-level randomization, we will adjust each model for additional pre-defined patient-level variables (age, sex, body mass index, LSA, number of ADLs/IADLs limitations, fear of / concerns about falling and muscle strength at baseline) to account for case-mix differences between groups in a sensitivity analysis. Moreover, we will assess imbalances of patient characteristics between groups. If we observe imbalances in covariates not considered in the sensitivity analysis, we will perform additional adjustments to assess the robustness of our results.

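### The main analysis of in-hospital accelerometer activity names no covariate; pre-specifying baseline DEMMI, which is already collected, would gain precision

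*SAP*

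**What the plan says.** - **Main model.** Section 6.2.1 says of the primary GEE that it "will be adjusted for the baseline LSA". For the other continuous outcomes the rule is: "Continuous secondary outcomes will be evaluated likewise, adjusting for the baseline value if applicable".
- **Activity outcomes.** Table 2 in section 6.1 lists two accelerometer outcomes, both typed as continuous. Item 11 is "Level of activity during hospitalization (% in light, moderate, [very] vigorous" and item 12 is "Level of activity during hospitalization (intensity of movement: vector magnitude CPM". Table 1 in section 5.4 has no baseline accelerometer variable, but it does list baseline DEMMI.
- **Sensitivity model.** Section 6.2.3 adjusts every model for a fixed set: "age, sex, body mass index, LSA, number of ADLs/IADLs limitations, fear of / concerns about falling and muscle strength at baseline". It then allows further adjustment for other covariates found to be imbalanced, without giving a threshold.
- **Readmissions.** "Readmissions and emergency room visits will be analyzed as time-to-event outcomes, except if we notice that those outcomes often happen multiple times". For the time-to-event version, "Time-to-event outcomes will be analyzed using a Cox regression model". No covariate is named for either version. Table 1 includes "Number of hospitalizations in the last 180 days before admission".

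**The concern.** The own-baseline rule works where the same instrument is used at day 0 and later. It gives nothing to an outcome that can only be observed during the stay. For items 11 and 12 the natural stand-in is DEMMI, the trial's own mobility scale. Under the same rule DEMMI is already the baseline covariate for DEMMI at discharge (item 8), but no pre-specified model for activity contains it. Section 6.4 does use all Table 1 variables, DEMMI included, as predictors for imputation, so the plan already treats it as informative.

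What is at stake is precision. With 12 wards, chance differences in case mix are larger than under individual randomization, which is the reason section 6.2.3 itself gives for adjusting. A prognostic covariate named in advance narrows the interval whether or not the arms look imbalanced. An adjustment that is triggered only by an observed imbalance does not do this reliably, and it is chosen after seeing the data.

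**Working it through.** **Inputs from the SAP (section 2.3).** 274 patients, 137 per arm, 12 wards. 2 × 137 = 274, and the mean ward size is m = 274/12 = 22.8. The sample size itself cannot be reproduced, because the SAP leaves its inputs to the protocol.

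**Assumed, not in the SAP.** Correlation r of baseline DEMMI with in-hospital activity: 0.3 or 0.5. ICCs: 0 to 0.10.

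**Step 1: DEMMI carries its own ward-level variation and explains activity at both levels.** Let D(ICC) = 1 + (m − 1) × ICC, and let the part of activity that DEMMI does not explain have an ICC of 0.02. Then

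SE ratio = √[ (1 − r²)·D(0.02) / ( r²·D(DEMMI ICC) + (1 − r²)·D(0.02) ) ]

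with D(0.02) = 1 + 21.83 × 0.02 = 1.437, D(0) = 1, D(0.05) = 2.09 and D(0.10) = 3.18.

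| r | DEMMI ICC 0 | 0.05 | 0.10 |
|---|---|---|---|
| 0.3 | √(1.307/1.397) = 0.97 | √(1.307/1.496) = 0.93 | √(1.307/1.594) = 0.91 |
| 0.5 | √(1.078/1.328) = 0.90 | √(1.078/1.600) = 0.82 | √(1.078/1.873) = 0.76 |

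Simulation with 4,000 runs per cell gave 0.97, 0.94 and 0.90 in the first row and 0.89, 0.81 and 0.77 in the second, so the formula and the simulation agree. The 0.02 is a residual ICC. In the last cell the ICC of activity as a whole is 0.25 × 0.10 + 0.75 × 0.02 = 0.04, so the largest gain belongs to a more clustered outcome.

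**Step 2: DEMMI explains only within-ward variation.** With a common ICC, the variance factor is [(1 − ICC)(1 − r²) + m·ICC] / [(1 − ICC) + m·ICC].

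| r | ICC 0.01 | 0.05 | 0.10 |
|---|---|---|---|
| 0.3 | 0.927 (SE −4%) | 0.959 (SE −2%) | 0.975 (SE −1%) |
| 0.5 | 0.797 (SE −11%) | 0.886 (SE −6%) | 0.929 (SE −4%) |

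**Step 3: in terms of power.** Take a difference with 80% power unadjusted. If DEMMI explains both levels equally (variance factor 1 − r²), power becomes 84% at r = 0.3 and 90% at r = 0.5. If it explains only within-ward variation at ICC 0.05, power becomes 82% and about 85%.

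**Step 4: gain over the section 6.2.3 model.** Suppose r = 0.5, and that the fixed set acts as a composite correlating a = 0.40 to 0.45 with activity and b = 0.6 to 0.7 with DEMMI (also assumed). The partial correlation is (0.5 − ab)/√[(1 − a²)(1 − b²)].

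- a = 0.40, b = 0.6: 0.26/0.733 = 0.35, so the SE falls by 1 − √(1 − 0.35²) = about 6 to 7%.
- a = 0.45, b = 0.7: 0.185/0.638 = 0.29, so the SE falls by about 4%.

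With no other covariate, the patient-level gain at r = 0.5 is 1 − √0.75 = 13%.

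**Step 5: readmissions.** This is a comparison of text. Item 20 covers readmissions up to D180, and Table 1 holds hospitalizations over the 180 days before admission. The own-baseline rule is written for continuous outcomes only, so it never reaches item 20. The fixed set in section 6.2.3 does not contain the variable either.

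**The case against.** The strongest reply is that the plan already handles case mix. Section 6.2.3 adjusts each model, activity and readmissions included, for seven pre-defined kinds of baseline variable and promises more if imbalance is seen. An unadjusted main model for a secondary outcome, backed by an adjusted sensitivity analysis, is acceptable practice. This stands in large part, and it rules out several stronger readings:

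- A reader might infer that activity is compared without any covariate, or that baseline mobility enters no activity model. Neither is so. The sensitivity set contains LSA, ADL/IADL limitations and muscle strength. What is absent is one instrument, DEMMI.
- A reader might infer that the unadjusted result is biased. Chance imbalance between randomized wards is random error, which a valid confidence interval covers.
- A reader might infer that prior hospitalizations can play no part in the readmission analysis. The imbalance clause could bring them in, though only after the data have been inspected and without a stated threshold.
- A reader might treat activity as the key test of whether the intervention changed behaviour. Section 1.1 is about low mobility in hospital, but Table 2 gives items 11 and 12 no special rank among 22 secondary outcomes.

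For readmissions the case is weaker still. Hazard ratios are non-collapsible, so adding a prognostic covariate changes the quantity estimated and not only its precision. The link to emergency room visits is indirect.

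The reply does not remove the point that the main activity model, whose result will be reported first, omits a covariate that is already in the database. The imbalance clause is no substitute for naming that covariate in advance.

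**Conclusion.** The point holds as a precision gain on secondary outcomes and no more. The primary outcome is adjusted for its own baseline and is not affected, and nothing in the SAP is invalid here. For items 11 and 12, adding baseline DEMMI to the main GEE would lower the standard error by roughly 3 to 20% for correlations of 0.3 to 0.5. The outer cells of the grid run from 1% (r = 0.3, within-ward only, ICC 0.10) to 24% (r = 0.5, DEMMI ICC 0.10). Against the section 6.2.3 model the gain is smaller, about 4 to 7% under the assumptions of step 4. All correlations and ICCs are assumed. If DEMMI turned out to be only weakly related to accelerometer activity, the gain would be negligible. The readmission part is correct on the text but secondary and optional.

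**What to change.** Before unblinding, add one sentence to section 6.2.1: the accelerometer outcomes (items 11 and 12) are adjusted for baseline DEMMI in the main GEE, and the model without it is reported as supportive.

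Optionally, add the number of prior hospitalizations (hosp_previous_n) to the section 6.2.3 adjustment set for readmissions (item 20), and state that the resulting hazard ratio is conditional on that covariate and need not equal the unadjusted one.

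The cost is SAP wording and one extra term per model. Both variables are already in Table 1, so no new data collection is needed. Patients with a missing covariate would drop out of the adjusted model unless it is imputed, so the sentence should also say how they are handled.

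### Binary, count, multinomial and Cox models lack the small-sample correction that the LSA model gets on the same 12 wards; with a z reference their 5% tests run at roughly 4–13%

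*SAP*

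**What the plan says.** Section 6.2.1 of the SAP specifies the primary model in these terms: "LSA will be analyzed using GEEs with Gaussian distribution, exchangeable correlation structure and robust standard errors with small sample correction". It then gives the reason: "This model accounts for the cluster design as well as for the small number of clusters". Section 4.3.1 repeats the correction in the estimand. The continuous secondary outcomes inherit it: "Continuous secondary outcomes will be evaluated likewise, adjusting for the baseline value if applicable".

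The paragraphs that follow in section 6.2.1 drop it:

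- Binary: "Binary outcomes will be analyzed using a GEE with a binomial distribution, a logit link, an exchangeable correlation structure and robust standard errors".
- Count: "Count outcomes will be analyzed using a GEE with a negative binomial distribution, a log link, an exchangeable correlation structure and robust standard errors".
- Time to event: a Cox model for which "we will use shared frailties for clusters as well as cluster robust standard errors".
- Discharge destination: "multinomial logistic regression with robust standard errors to account for clustering".

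No other section extends the correction to these four model classes, and none states degrees of freedom or a t or normal reference for them. Section 2.3 gives 12 clusters in total, and section 4.1 promises 95% intervals and two-sided 5% tests throughout.

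**The concern.** The number of wards limits every model in the trial, not only the Gaussian one. A robust (sandwich) variance estimated from about six clusters per arm is biased low, and a normal reference ignores how imprecisely that variance is estimated. The SAP recognizes the problem for one outcome type and leaves it open for the rest. An analyst who follows the text could run default robust errors for depression, pressure ulcer, delirium, fall-risk drugs, falls, emergency visits, readmissions, institutionalization, death and discharge destination. Those intervals would stand beside corrected intervals for the continuous outcomes under the same 95% label, and chance findings on these outcomes would be more frequent than stated.

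**Working it through.** **Inputs from the SAP.** 12 wards and 274 patients, 137 per arm (section 2.3); 1:1 ward allocation, hence 6 wards per arm and 274/12 = 22.8 patients per ward; two-sided 5% (section 4.1). On allocation, section 2.2 says: "Randomization was blocked with block size two and stratified by hospital"; it also stratifies by ward size. The derivation of 274 is left to the protocol, and nothing here depends on it.

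**Assumptions, because the SAP gives no figures.** Reference distribution, intracluster correlation (ICC), share of the ICC lying between hospitals, event rates, ward sizes, and four wards in each of the three hospitals. Ward-size strata were not modelled.

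**Step 1: closed form.** Take six equal wards per arm and approximately normal ward summaries. The sandwich divides each arm's sum of squares by 6 where the unbiased estimate divides by 5, so it is 5/6 of the unbiased variance. The statistic with the unbiased variance follows t on 12 − 2 = 10 degrees of freedom. With critical value c and any extra variance factor f, the true level is P(|t10| > c × √(5/6 × f)).

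| Variance | Reference | Threshold on t10 | True level |
|---|---|---|---|
| Plain sandwich | z | 1.96 × √(5/6) = 1.789 | 10.4% |
| Software factor 12/11 | z | 1.96 × √(5/6 × 12/11) = 1.869 | 9.1% |
| Plain sandwich | t10 | 2.228 × √(5/6) = 2.034 | 6.9% |
| Corrected by 6/5 | z | 1.960 | 7.8% |
| Corrected by 6/5 | t10 | 2.228 | 5.0% |

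This needs no ICC or event rate. Both parts, variance and reference, are needed to reach 5%.

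**Step 2: binary outcome, paired randomization within three hospitals.** 72 scenarios of 20,000 trials: rate 5–30%, ICC 0.01–0.05, 0, 50 or 80% of the ICC between hospitals, wards equal or sized 8–40.

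- Uncorrected, z: 4.0–12.9%, median 9.0%, above 5% in 71 of 72.
- Uncorrected, t10: 2.0–8.7%, median 5.8%.
- Variance corrected by 6/5, t10: 1.1–6.3%, median 4.0%.

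**Step 3: fitted exchangeable logistic GEE, z** (2,000 trials each, rate 20%, ICC 0.03). At hospital share 0/50/80%: 10.3/7.8/6.7% with equal wards and 12.6/10.1/9.3% with unequal wards. Some fits stopped at the iteration limit and were kept.

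**Step 4: the other models, z.**

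- Count (negative binomial data, log link, independence weights in place of exchangeable): 9.9–12.9%; 8.6–11.5% with the 12/11 factor.
- Multinomial, three categories, single coefficients, cluster-robust: 6.9–12.1%. With the 12/11 factor and four or six categories: 3.7–11.5%. A joint test is worse: 20–25% with four categories and 35–46% with six.
- Cox with cluster-robust errors and no frailty: 5.3–12.3%.
- Gamma frailty plus robust errors, approximated with an exponential baseline and a moment estimate of the frailty variance: 9.4–11.5%; 8.2–10.1% with the 12/11 factor.
- Shared-frailty Cox with its own model-based errors, equal wards: 10.3/5.5/4.3% at hospital share 0/50/80%.

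Over wider assumptions (prevalence 3–40%, ICC up to 0.10, wards of 10–37), single-coefficient levels ran from about 3 to 15%, mostly 8–12%. The low end comes from rare outcomes, or from hospital differences that stratification balances but the model ignores.

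**Step 5: after a leverage-based (Kauermann–Carroll) correction with t10.** Binary: 4.3–5.7% with equal wards and prevalence of at least 10%, 5.4–7.5% with unequal wards. Counts: 4.4–6.2%.

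**The case against.** The best counter-argument is that much of the excess comes from the normal reference, which the SAP does not state and which is assumed here. That is right in part. Adding only a variance correction moves the closed form from 10.4% to 7.8%, and an uncorrected test with t10 has a simulated median of 5.8%, about 1.2 times nominal. The range in the heading is therefore conditional on z, and the fix must name the reference as well as the correction. For the same reason, that the LSA model is untouched means only that its sentence carries the correction; the SAP does not say which correction or which degrees of freedom it uses.

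The evidence is also uneven. It is strong for the binary GEE. The count and frailty-plus-robust results rest on approximations, and fits that did not converge were kept although section 6.2.3 would send them to a mixed model.

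Stratification by hospital lowers the figure when hospitals differ, as the simulations show. The mixed models of section 6.2.3 are a useful cross-check, but only as a sensitivity analysis or convergence fallback, and no small-sample degrees of freedom are stated for them either.

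Finally, all affected outcomes are secondary and no stopping rule depends on them. That limits the weight of the point but does not justify intervals that miss their stated coverage.

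**Conclusion.** The concern holds: section 6.2.1 is wrong as written for four model classes. Followed literally with a normal reference, single-coefficient 5% tests run at roughly 4–13%, with a median of 9.0% for binary outcomes, which is 9.0/5 = 1.8 times nominal. With t10 but no variance correction the excess is small on median (5.8%) and reaches 8.7%. The textual gap and the binary result are firm; confidence is moderate for the count, multinomial and Cox models. The sizes depend on assumed ICCs, hospital shares, ward sizes and event rates. In unfavourable but plausible corners (rare events, most of the ICC between hospitals) the uncorrected test can be close to or below 5%. This should be fixed, but it does not threaten the primary analysis.

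**What to change.** In section 6.2.1, add to the binary and count GEE sentences that they use the same small-sample-corrected robust standard errors as the primary analysis, with the correction named, and a t reference with degrees of freedom based on the number of wards. Since the LSA sentence does not name its correction either, name it there once and refer back to it.

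For the Cox and multinomial models, state an equivalent correction for the number of clusters with a t reference, or state that their errors are uncorrected and that their intervals may be too narrow with 12 wards. Outcome definitions and the frailty term can stay as they are.

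The cost is SAP wording, a covariance option in the GEE code and, for Cox and multinomial, either a short custom variance step or the limitation sentence. Intervals become up to about 25% wider (2.228/1.96 × √(6/5) = 1.245). The tests become somewhat conservative, down to 1.1% in the simulations, if most of the ICC lies between hospitals. Settling this before database lock avoids a choice made with the results in view.
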